5.6 Safety Analyses

5.6.1 Extent of Exposure

Any analysis related to the exposure will be based the SS.

The number and percentage of participants with cumulative IMP duration (e.g. any duration, ≥ 1 week, ≥ 2 weeks, ≥ 3 weeks,, etc.) will be presented by IMP.

IMP duration = Date of Last Dose – Date of First Dose +1

The duration of exposure to each treatment will be summarized by IMP:

Duration of exposure in years (or Participant Exposure Years (PEY)) = $[(\min(\text{Date of Last Dose} + 40 \text{ days, Last Visit}) - \text{Date of First Dose} + 1)] / 365.25$

Thus, exposure will be adjusted for the 5 half-lives of active treatment which is 40 days.

Duration of exposure (100 participant years) = PEY / 100.

Summaries on the treatment exposure and time at risk in subject years will be given.

Participants which are exposed to both treatments will be presented in either study treatments using the corresponding start and stop treatment date.

The number of doses missed (from the eCRF Study drug administration page after Day 1) will be summarized overall and by IMP.

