- Non-Serious TEAEs by PSOC and PT of at least 5% within any IMP (Main Portion) or active treatment (Extension Portion), in SS
- TEAEs by PSOC and PT leading to drug discontinuation, in SS
- TEAEs by PSOC and PT leading to death, in SS

Of note, the following are not considered to be AEs despite requiring hospitalization:

- Pre-existing conditions that, in the opinion of the investigator, did not worsen or progress during study participation
- Routinely scheduled procedures or treatments
- Elective procedures that were scheduled prior to study participation (i.e., signing of the ICF)

Safety tables for the combined Main and Extension Portion of the study, will display the Treatment Emergent Adverse Event Incidence Rate (AEIR) per 100 patient-years of Zilucoplan treatment (thus no placebo arm to be summarized due to limited exposure time as compared to active). Tables will include the PEY per 100 patient years (as defined in Section 5.6.1), number and percentage of participants with a particular TEAE, the exposure adjusted incidence rate (EAIR) followed by 95%CI and the exposure adjusted event rate (EAER):

- EAIR for TEAEs by PSOC and PT, in SS
- EAIR for serious TEAEs by PSOC and PT, in SS

The EAIR is defined as the number of study participants with a specific new TEAE divided by the duration of exposure of all participants (scaled to 100 participant years). The time at risk for a study participant is censored at the date of this event. If a study participant has no events, the total time at risk (i.e. exposure) is used.

Exact Poisson 95% CIs for EAIR are calculated using the relationship between the Poisson and the Chi-square distribution (Ulm, 1990; Fay and Feuer, 1997):

$$\text{Lower Confidence Limit} = x_{2n,\alpha/2}^2/2$$

$$\text{Upper Confidence Limit} = x_{2n(n+1),1-\alpha/2}^2/2$$

where n stands for the number of participants with a specific TEAE for the incidence rate of interest and is the basis for the number of the degrees of freedom for the chi-square quantile for the upper tail probability χ^2 .

The EAER is defined as the total number of TEAEs including repeat occurrences in individual study participants divided by the total time at risk scaled to 100 patient-years. No confidence interval will be computed for the EAER.

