Should an Adverse Event of Interest has not occurred during the study, the corresponding line should be included with zero occurrences.

The following tables will be created:

- TEAEs of interest by PT, in SS,
- EAIR for TEAEs of interest by PT, in SS (combined Main and Extension Portion among participant received at least one dose Zilucoplan).

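### The printed 95% CI for the exposure-adjusted incidence rate is never divided by time at risk, so it bounds a count and not the rate; its upper degrees of freedom also read 2n(n+1) where 2(n+1) is needed

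*SAP*

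**What the plan says.** SAP Section 5.6.2 gives the point estimate as a rate: "The EAIR is defined as the number of study participants with a specific new TEAE divided by the duration of exposure of all participants". Each participant's time at risk ends at the event, and Section 5.6.1 fixes the unit: "Duration of exposure (100 participant years) = PEY / 100".

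The interval is introduced as an interval for that rate: "Exact Poisson 95% CIs for EAIR are calculated using the relationship between the Poisson and the Chi-square distribution". The two limits are then printed as

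- lower: "Lower Confidence Limit} = x_{2n,\alpha/2}^2/2"
- upper: "Upper Confidence Limit} = x_{2n(n+1),1-\alpha/2}^2/2"

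The text below them explains n as a participant count: "where n stands for the number of participants with a specific TEAE for the incidence rate of interest". It also describes the chi-square quantile in terms of an upper tail probability.

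The EAIR is planned for the combined Main and Extension tables of TEAEs and serious TEAEs (Section 5.6.2) and for AEs of interest (Section 5.6.3: "EAIR for TEAEs of interest by PT, in SS"). Section 5.6.3 also says: "Should an Adverse Event of Interest has not occurred during the study, the corresponding line should be included with zero occurrences".

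**The concern.** Two things are wrong with the formula as it stands.

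1. **Scale.** The EAIR is a count divided by exposure, but both limits are functions of n alone. They bound the expected number of affected participants. Sections 5.6.1 to 5.6.3 contain no sentence that divides them by exposure.
2. **Degrees of freedom.** The exact Poisson upper limit uses 2(n+1). The text reads 2n(n+1).

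The combined tables show zilucoplan only, with no placebo column, so this interval is the only measure of uncertainty planned beside each rate. For a rare event such as Neisseria infection the likely count is zero. The upper limit is then the informative number, because it shows how large a rate is still compatible with the data.

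**Working it through.** **Inputs.** The 95% level (0.025 per tail), n, the EAIR definition and the unit of 100 PY come from SAP Sections 5.6.1 and 5.6.2. The planned size of about 24 participants comes from SAP Section 1.2. The documents give no total exposure, so 10, 20 and 40 PY are assumed. Spread over 24 participants these are means of 5, 10 and 20 months on zilucoplan (for example 10 × 12 / 24 = 5). The SAP prints no worked limits to reproduce; the figure to test against is its nominal 0.025 in each tail.

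**Formulas.** Write χ²(p; df) for the quantile with cumulative probability p, and T for total time at risk in units of 100 PY.

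- As printed: lower = χ²(0.025; 2n)/2; upper = χ²(0.975; 2n(n+1))/2.
- Exact Poisson limits for a rate: lower = χ²(0.025; 2n)/(2T), or 0 if n=0; upper = χ²(0.975; 2(n+1))/(2T).

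**Step 1: scale, with the degrees of freedom out of the picture.** At n=1, 2n(n+1) = 2(n+1) = 4, so the subscript question does not arise. The printed interval is 0.03 to 5.57 whatever the exposure. Dividing by T gives:

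| n | Exposure (PY) | EAIR per 100 PY | As printed | Correct |
|---|---|---|---|---|
| 1 | 10 | 10.0 | 0.03–5.57 | 0.3–55.7 |
| 1 | 20 | 5.0 | 0.03–5.57 | 0.1–27.9 |
| 1 | 40 | 2.5 | 0.03–5.57 | 0.1–13.9 |
| 3 | 10 | 30.0 | 0.62–19.68 | 6.2–87.7 |
| 3 | 20 | 15.0 | 0.62–19.68 | 3.1–43.8 |
| 3 | 40 | 7.5 | 0.62–19.68 | 1.5–21.9 |

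Undivided limits are on the rate scale only when T = 1, that is, when time at risk is exactly 100 PY.

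**Step 2: when the interval misses its own estimate.** The EAIR is 100n/PY, so it lies above the printed upper limit when PY < 100n/upper. This gives 100/5.57 = 17.9 PY at n=1, 200/11.67 = 17.1 at n=2, 300/19.68 = 15.2 at n=3 and 500/41.65 = 12.0 at n=5. If the degrees of freedom are really 2(n+1) and only the division is missing, n=3 gives 0.62 to 8.77, and the threshold rises to 300/8.77 = 34.2 PY.

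**Step 3: degrees of freedom alone, on the count scale.** At a correct upper limit U, P(X ≤ n) for a Poisson mean of U equals 0.025.

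| n | Upper, 2(n+1) df | Upper, 2n(n+1) df | P(X ≤ n) at the 2n(n+1) limit |
|---|---|---|---|
| 0 | 3.69 | 0 df, no usable limit | – |
| 1 | 5.57 | 5.57 | 0.025 |
| 2 | 7.22 | 11.67 | 0.0007 |
| 3 | 8.77 | 19.68 | 0.000004 |
| 5 | 11.67 | 41.65 | 1e-12 |

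With 2(n+1) the probability is 0.025 at every n.

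**Step 4: zero events.** The correct upper limit is 3.69/T: 36.9, 18.4 and 9.2 per 100 PY at 10, 20 and 40 PY. The printed formula has 0 degrees of freedom at n=0.

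**Step 5: tail convention.** The printed subscripts, α/2 for the lower limit and 1−α/2 for the upper, work as cumulative probabilities. Read as upper-tail probabilities, n=3 would give a lower limit of 7.22 and an upper limit of 1.09 even with 2(n+1) degrees of freedom.

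**The case against.** The best defence is that the intent is plain. The SAP names an exact Poisson interval for the EAIR, cites two method papers and sets the interval beside a rate, so an experienced programmer would divide by the same denominator. That may well happen, and the table specifications, a separate document not available here, may already do it. It does not rescue the SAP, which prints an explicit formula that gives a wrong interval when followed.

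The degrees of freedom rest on a formula read by a program from a PDF, and other formulas in this SAP came through damaged. A stray n in the subscript is possible, so this part is conditional on the source PDF. If the subscript is in fact 2(n+1), the n=0 limit of 3.69 is recovered on the count scale. The missing division remains, because a reading fault would have had to drop a denominator from both lines together with its definition.

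Three further points are fair:

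- The printed interval does not always miss its own estimate. For n=1, 2, 3 and 5 it contains the EAIR at 20 and 40 PY, and at n=3 and 40 PY the upper limits, 19.68 and 21.9, are close because the two errors pull in opposite directions. Exposure may well exceed 17.9 PY (about 9 months each for 24 participants), since the Extension runs 18 months in France and is open-ended elsewhere (Protocol Section 7.2).
- Section 5.6.3 requires a zero line for AEs of interest but does not say in terms that a CI appears on it.
- The tail wording is a matter of clarity, since the subscripts themselves point to the right convention.

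**Conclusion.** The concern holds: the formula is wrong as written. The missing division is certain on the text and independent of how the subscript reads. The degrees-of-freedom error is certain only if the PDF shows 2n(n+1).

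The size depends on an exposure total that the documents do not give. Over the assumed 10 to 40 PY, the correct upper limit at n=1 is 13.9 to 55.7 per 100 PY, against a printed 5.57. That is a factor of 1/T, from 2.5 to 10. For n≥2 the inflated degrees of freedom partly offset the missing division, so correcting the subscript alone would make the upper limit worse at these exposures. Both changes are needed together.

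The reach is limited to the EAIR intervals for TEAEs, serious TEAEs and AEs of interest in the combined zilucoplan tables. Event percentages, the exposure-adjusted event rate (for which no CI is planned) and all efficacy results are untouched, and no decision rule uses these intervals. It should be corrected, but it does not threaten the trial's main conclusions.

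**What to change.** Replace the two formula lines in SAP Section 5.6.2 with:

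- lower limit = χ²(α/2; 2n) / (2T), set to 0 when n=0;
- upper limit = χ²(1−α/2; 2(n+1)) / (2T);

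where T is total event-censored time at risk in units of 100 participant-years, the same denominator as the EAIR, and χ²(p; df) is the quantile with cumulative (lower-tail) probability p. Remove the reference to an upper tail. State in Section 5.6.3 that zero-occurrence lines in the EAIR table carry the upper limit.

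Check the subscript in the source PDF, and check that the table specifications and code match the corrected formula. The cost is two formula lines, two clarifying sentences and a programming check. No new data are needed and no efficacy analysis changes.

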5.6.3 Adverse Events of Interest

The following bullets define the TEAEs of interest for Zilucoplan:

- **Infections**
 - Serious infections: Serious TEAEs in MedDRA SOC “Infections and infestations”
 - Infections: TEAEs in MedDRA SOC “Infections and infestations”
 - Neisseria infections: TEAEs in MedDRA HLT “Neisseria infections”
 - Serious Neisseria infections: Serious TEAEs in MedDRA HLT “Neisseria infections”
- **Adverse events potentially related to hypersensitivity (including anaphylaxis)**

Potential anaphylactic reactions are defined via a MedDRA algorithmic approach (see Section 6.2), which combines a number of different TEAEs/anaphylactic reaction symptoms. Some cases are dependent on the presence of multiple symptoms/TEAEs (i.e. TEAEs with the same AE onset day or one day later) in order to be classified as an anaphylactic reaction; at least one of the symptoms/TEAEs needs to be serious for the reaction to be classified as a serious anaphylactic reaction.

- Anaphylactic reactions are defined as follows:
 - Serious Anaphylactic reactions: MedDRA algorithmic approach to anaphylaxis where at least one of the TEAEs needs to be serious
 - Anaphylactic reactions: MedDRA algorithmic approach to anaphylaxis among TEAES
- Hypersensitivity reactions are defined as follows:
 - Serious hypersensitivity reactions: Serious TEAEs in MedDRA Standardized MedDRA Query (SMQ) “Hypersensitivity (narrow scope)”

Hypersensitivity reactions: TEAEs in MedDRA SMQ “Hypersensitivity (narrow scope)”

- **Injection site reactions**
 - TEAEs in MedDRA HLT “Injection site reactions” or HLT “Administration site reactions NEC”.
- **Hepatic events and drug-induced liver injuries, Drug related hepatic disorders**
 - TEAEs in MedDRA SMQ narrow scope of “Drug related hepatic disorders - comprehensive search (SMQ)” excluding the 2 sub-SMQs of “Liver neoplasms, benign (incl cysts and polyps) (SMQ)” and “Liver neoplasms, malignant and unspecified (SMQ)”.
- **Malignancies**
 - Malignant or unspecified tumours: TEAEs in MedDRA SMQ “Malignant or unspecified tumours (SMQ)”
 - Malignant tumours: TEAEs in MedDRA SMQ “Malignant tumours (SMQ)”

Note: the events included in the “Malignant tumours” table will be a subset of the events included in the “Malignant or unspecified tumours” table. While the “Malignant tumours (SMQ)” is most relevant, “Malignant or unspecified tumours (SMQ)” will be reviewed for potential malignancies.

Should an Adverse Event of Interest has not occurred during the study, the corresponding line should be included with zero occurrences.

The following tables will be created:

- TEAEs of interest by PT, in SS,
- EAIR for TEAEs of interest by PT, in SS (combined Main and Extension Portion among participant received at least one dose Zilucoplan).

5.6.4 Additional Safety Assessments

Further safety assessments include laboratory data, vital signs and 12 Lead ECG. Details of analysis are written further below. All analysis will be based on the SS.

5.6.4.1 Clinical laboratory evaluations

The following table lists all hematology, chemistry, urinalysis and coagulation analytes collected throughout the study, using a central laboratory according to the schedule of the study protocol.

Table 5-1: Laboratory Assessments

Chemistry	Hematology
Alanine aminotransferase (ALT)	Hematocrit
Albumin	Hemoglobin

Table 5–1: Laboratory Assessments

Chemistry	Hematology
Alkaline phosphatase (ALP)	Mean corpuscular hemoglobin (MCH)
Amylase	Mean corpuscular hemoglobin concentration (MCHC)
Aspartate aminotransferase (AST)	Mean corpuscular volume (MCV)
Aldolase	Platelet count
Blood urea nitrogen (BUN)	Red blood cell (RBC)
C-reactive protein (CRP)	White blood cell (WBC) count and differential:
Calcium	Basophils (% and absolute)
Chloride	Eosinophils (% and absolute)
Creatinine	Lymphocytes (% and absolute)
Creatine Kinase (CK)	Monocytes (% and absolute)
Gamma-glutamyl transferase (γ -GT)	Neutrophils (% and absolute)
Glucose	Coagulation (among participants receiving anticoagulant treatment)
Lactate dehydrogenase (LDH)	International normalized ratio (INR)/prothrombin time (PT)
Lipase	Partial thromboplastin time (PTT) or activated partial thromboplastin time (aPTT)
Potassium	
Sodium	
Total bilirubin (TBL)	Urinalysis
Total protein	pH, specific gravity, protein (qualitative), glucose (qualitative), ketones (qualitative), bilirubin (qualitative), urobilinogen, occult blood, hemoglobin, cells and microscopic examination (if necessary).

5.6.4.1.1 Laboratory values over time

All laboratory values listed at Table 5–1 of Section 5.6.4.1 will include on treatment data for analysis defined as the values after the first dose of the study drug until on or before the last dose plus 40 days (or last visit depending which occurs first). At all tables, laboratory assessments will be sorted by panel (chemistry, hematology, coagulation, urinalysis). Within each panel the assessments will be sorted alphabetically.

Summaries on Markedly Abnormal (MA) values will also be provided for the Main portion by scheduled visit and overall (including unscheduled visits) and for the Extension portion by scheduled visit and overall (including unscheduled visits), for each IMP. MA criteria are listed at Section 6.1.7, Table 6–3 MA criteria are defined by Grade 3 or higher events according to the Common Terminology for Adverse Events (CTCAE), Version 5.0, November 17, 2017 unless otherwise noted.

All laboratory test results will be listed, including baseline, scheduled and unscheduled visits with results in standard units. Values outside the reference range for the continuous variables will be flagged in the listings. The reference ranges will also be displayed. In addition, the

listings will include a flag for values identified as MA. Additional lab test for pregnancy testing, will also be listed.

5.6.4.1.2 Individual Subject Changes of Laboratory Values

The laboratory variables that are categorized as normal, high or low based on the reference range as supplied by the analytical laboratory will be presented in shift tables from baseline to each scheduled post-baseline visit by IMP and any post-baseline visit (including unscheduled visits) by IMP.

The number and percentage of participants who meet the criteria with respect to elevated liver function tests and drug-induced liver injuries (PDILI) will be summarized by IMP at each scheduled visit and at any visit (including unscheduled visits), [Table 6-4](#) in Section [6.1.7](#). A listing will also be provided for participants who meet at least one of the criteria.

5.6.4.2 Vital Signs

The vital signs assessed are the Heart Rate, the Body Temperature and the Systolic and Diastolic Blood Pressure, all in sitting position.

5.6.4.2.1 Vital Sign Values Over Time

Vital signs summaries will only include on treatment data defined as those measurements after the first study treatment dose until the day of the last dose plus 40 days (or last visit depending which occurs first).

Analysis will be performed descriptively for the change from baseline to each post baseline visit by IMP. Change from baseline of each vital sign parameter will be summarized only among participants with both baseline and post baseline values:

Change from Baseline = post Baseline – Baseline value

Summaries of vital sign abnormalities will be created for the Main and Extension portion by scheduled visit and overall (including unscheduled visits) for each IMP. Criteria for vital sign abnormal values are shown in [Table 6-5](#), Section [6.1.7](#).

A by-participant listing of all vital sign measurements at each visit and change from baseline will be presented by IMP and visit. The listing will include a flag for values identified as abnormal.

5.6.4.2.2 Individual Subject Changes of Vital Sign Values

A by patient listing will be provided (assessing scheduled and unscheduled visits), capturing for each vital sign parameter of the participants with at least one abnormality in the value post-baseline. Results obtained for the vital sign parameters will be displayed.

5.6.4.3 Electrocardiograms

The following assessments will be summarized and reported: PR interval, RR interval, QRS duration, QT interval, QT corrected for heart rate using Fridericia's formula ($QTcF = QT/RR^{1/3}$).

5.6.4.3.1 Electrocardiogram Values Over Time

ECG summaries will only include on treatment data defined as those measurements after the first study treatment dose and on or before the last dose plus 40 days (or last visit, depending which occurs first).

Analysis will be performed descriptively for the change from baseline to each post baseline visit by IMP. Change from baseline of each ECG parameter, will be summarized only among participants with both baseline and post baseline values:

Change from baseline = post baseline – baseline value

Summaries of ECG abnormalities will be created for the Main and Extension portion by scheduled visit and overall (including unscheduled visits) for each IMP. Criteria for ECG abnormalities values are listed in [Table 6–6](#) in Section [6.1.7](#).

A by-participant listing of all ECG measurements when performed and change from baseline will be presented by IMP and visit. The listing will include a flag for values identified as based on the abnormality criteria.

5.6.4.3.2 Individual Subject Changes of Electrocardiograms Values

The ECG that are categorized as normal, high or low based on the reference range in shift tables from baseline to each scheduled post-baseline visit by IMP and any post-baseline visit (including unscheduled visits) by IMP.

A by patient listing will be provided (assessing scheduled and unscheduled visits), capturing each of the 12 Lead ECG parameters of the participants with at least one abnormal value post-baseline based on the abnormality criteria. Results obtained for the ECG parameters will be displayed.

5.6.4.4 Other safety endpoint(s)

5.6.4.4.1 Physical examination

Any clinically significant abnormalities in physical examination will be reported as AEs when appropriate with reference the period after the first administration of study dose until the last day of study dose administration plus 40 days (or last visit, depending which occurs first).

5.6.4.4.2 Immunogenicity

Blood samples for ADA assessment will be collected prior to dose administration at baseline (screening data will be considered as baseline data for ADA assessments), Day 8, Day 29 and Day 57 as well as Day E8, Day E28, Day E57, Day E117 and every 3 months after, including

final Extension visit in all participants prior to drug administration. These samples will be used to investigate and characterize any ADA response over time in SS.

- Sample values that are either ‘negative screen’ or ‘positive screen’ and ‘negative immunodepletion’ will be defined as **ADA negative**
- Sample values that are ‘positive screen’ and ‘positive immunodepletion’ will be defined as **ADA positive**
- Samples that could not be tested for ADA status due to inadequate sample volume, mishandling, or errors in sample collection, processing, storage, etc, will be defined as **Missing**

Sample neutralizing antibody (NAb) status (positive/negative/missing) will be determined for ADA positive samples.

The following ADA classifications will be derived from the sample ADA status:

Table 5–2: ADA Classification

Classification	Classification Label	Definition
1	Pre-ADA negative – treatment induced ADA negative	Participants who are ADA negative at baseline and ADA negative at all sampling points post-baseline.
2	Pre-ADA negative – treatment induced ADA positive	Participants who are ADA negative at baseline and ADA positive at any sampling point post-baseline. It also includes participants who have a missing pre-treatment sample (either missing or insufficient volume) at baseline with one or more ADA positive post-baseline samples.
3	Pre-ADA positive – treatment reduced ADA	Participants who are ADA positive at baseline, and ADA negative at all sampling points post-baseline (including the Extension Portion of the study).
4	Pre-ADA positive – treatment unaffected ADA	Includes participants who are ADA positive at Baseline and ADA positive at any sampling point post-Baseline (including Extension Portion) with titer values of the same magnitude as baseline (less than a predefined fold difference from the baseline value which will be defined within the validation of the assay, i.e. minimum significant ratio of the assay).
5	Pre-ADA positive – treatment boosted ADA positive	Includes participants who are ADA positive at Baseline and ADA positive at any sampling point post-Baseline (including Extension Portion) with increased titer values compared to baseline (greater than a predefined fold difference increase from Baseline value which will be defined within the validation of the assay i.e. minimum significant ratio of the assay).

Classification	Classification Label	Definition
6	Inconclusive	Participants who have an ADA positive Baseline sample and some post-Baseline samples are missing, while other post-Baseline samples are ADA negative.
7	Treatment emergent ADA positive	Combination of 2 and 5.
8	Pre-ADA positive	Combination of 3, 4, and 5.

In addition to the ADA classifications above, for the purpose of evaluations of the impact of ADA on plasma concentrations and efficacy and safety endpoints, the following definitions will be used:

- Cumulative ADA status (positive/negative). If a participant had at least one positive sample at any time point up to and including the given time point, that participant will be counted as positive at that time point, regardless of any subsequent negative measurements. Thus, the number of participants included in the summary of positive and negative samples will vary by time point for each IMP.
- Overall ADA status. A participant will be classified as overall ADA Positive if at least one post-baseline measurement is positive. A participant will be classified as overall ADA negative if at all post-Baseline visits the ADA status is Negative.

The ADA of Zilucoplan will be measured using a three-tiered assay approach: screening assay, confirmatory assay and titration assay. Any sample confirmed positive for ADA will be assayed to determine whether there is neutralizing potential.

The following tables will be presented on the SS.

- Number and percentage of participants with positive, negative or missing sample ADA status at the time of each visit and all visits by IMP.
- Number and percentage of participants in each of the ADA classifications presented in [Table 5-2](#) by IMP.
- Number and percentage of participants in each of the NAb classifications presented in [Table 5-2](#) by IMP.
- The prevalence of immunogenicity (Classification 2, 3, 4 and 5), defined as the (cumulative) proportion of participants having ADA positive samples (including pre-ADA positive) at any point up to and including that time point will be summarized by IMP and total. Missing samples will not be included in the denominator.
- The same table will be repeated for Nab (cumulative and overall Nab status will be defined as described above for ADA).
- The first occurrence of treatment-emergent ADA positive will be summarized using frequency and percentage at each post-baseline visit by IMP group. Participants will be counted only once in the numerator based on the earliest visit at which treatment-emergent

ADA positivity is observed. At other visits, participants will be counted in the denominator (assuming a measurement is available). Missing measurements will not be included in the denominator.

- A summary table of all immune related TEAEs by ADA status will be presented by IMP group. For this summary, participants will be presented for TEAEs occurring prior to becoming treatment emergent ADA positive, TEAEs occurring after becoming TE ADA positive and TEAEs for participants who remained TE ADA negative (classifications 1,3,4).
 - Notes: Study physician/safety physician/safety lead will mark the Preferred Term of immune related AEs based on an excel output of all TEAEs (blinded) after database lock. The marked AEs will be used for the summary.

The results for the ADA assessments will be listed by IMP group and timepoint, including the screening assay, confirmatory assay, ADA titer, NAb titer, PK concentration, change from Baseline, treatment-emergent ADA status and ADA classifications. In addition, time since administration of IMP will be reported (in days).

A TEAE overview table will be presented for active treatment by ADA status. Additionally, the number and percentage of participants who experience some AEs (Hypersensitivity reactions, injection sites reactions as defined in Section 5.6.3 and autoimmune disorders) will be presented by SOC and PT and by ADA Status. Autoimmune disorders will be defined if HLT is in “Autoimmune disorders”. For these summaries, participants will be presented for TEAEs occurring prior to becoming treatment emergent ADA positive, TEAEs occurring after becoming treatment emergent ADA positive, and TEAEs for participants who remained TE ADA negative (classifications 1,3,4,6).

